to achieve their health goals through lifestyle and behavior adjustments. The health coach for this project, will have experience with chronic [back] pain and depression. The Health coaches will receive extensive training on how to deliver the content to older veterans with depression and chronic back pain. These prerequisites will ensure that the health coach has exposure to principles of motivational interviewing, patient activation, and goal setting. The health coach will receive additional training in motivational interviewing and delivery of the proposed intervention as intended, with the use of an intervention manual. Furthermore, the health coach(es) will complete all required credentialing paperwork and security training. As proposed in Figure 1, the intervention will be delivered via telephone by health coaches using modules that target the listed potential behavioral determinants that specifically focus on how older adults are uniquely motivated to change. The health coaches will educate participants, use motivational interviewing to enhance perceived benefits, reduce barriers to participating in recommended behaviors, and assess motivations and readiness to change. Once a participant is ready for action, health coaches will use motivational coaching as well as goal setting and action planning techniques to facilitate behavioral change.

In Aim 1 of this research we developed a behavioral change intervention, using input and feedback from national experts, other stakeholders, and Veterans. In Aim 2 of this study we recruited a small sample (n=7) of Veterans and pre-tested the roll out of the intervention. We developed study procedures including recruitment procedures, intervention progress tracking, fidelity assessments, outcomes assessments on redcap, and hiring and training of research staff. Using feedback from the health coach, research staff, Veterans, and primary care providers we have modified the intervention manual and procedures, iteratively. This Aim 3 protocol is intended to evaluate the intervention in a larger sample, including a randomized design that includes a waitlist control group.

If referring to the VA CDA-2 Research Plan, please focus only on Aim 2. Aim 1 has already been IRB approved (#16-024). A separate IRB submission will address Aim 3.

7. Definition of the Population to Which the Study is Directed, with Justification

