A protocol will be in place should the study team identify a potential participant who reports or develops suicidal ideation. For safety purposes, the protocol is as follows: Any patient identified as having suicidal ideation during this screening process will be referred to [name] and will be referred to the VA suicide hotline that involves warm transfers to mental health professionals. Using a pre-established protocol, [name] will contact the subject and make arrangements for immediate mental health assessment and treatment based on the subject's symptoms. All suicidal patients will be provided with the VA suicide crisis hotline number, regardless of other immediate clinical interventions. Furthermore, subjects with severe psychiatric diagnoses (as specified among the exclusion criteria) or prior documented inpatient admissions for suicidal ideation will be excluded and not enrolled in the study.

Randomization: Once the baseline assessment has been completed, eligible participants will be randomly assigned to the waitlist control group (n=25) or the intervention (n=25) by applying a set of computer-generated random numbers. Since we are interested in better understanding feasibility of the intervention as compared to the waitlist control, and how behaviors are sustained over time, Aim 3 involves extended follow-up to 12-months. We will use these extended follow-up data to better understand differential attrition as well as preliminary formative implementation evaluation (see below).

At this time, a binder with the intervention manual material will be sent to the subject's home if randomized to the intervention arm. This manual is intended for the patient to follow along with the health coach during phone calls. It will also contain the activity trackers that he/she will use in between session to track activity, step counts, and impact on pain and depression.

We will mail out appointment letters before each intervention visit. Depending on the content of the session, these reminders may also include a list of the subject's values, goals and action plan. The patients will also be called by a research team member or the health coach prior to the scheduled phone calls as a reminder. During Aim 2, we learned that some patients are forgetful about the timing of the phone calls which causes delays-these phone call reminders were helpful.

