The health coaches will deliver the 8 (8 modules +3 check-in calls during the goal setting modules) session telephone-based intervention to 25 subjects randomly assigned to the intervention arm. For subjects assigned to the comparator arm (n=25), the "wait-list" control group, they will continue receiving usual care for both cLBP and depression, but not the active intervention.

A research member, not the health coach, will call all subjects regardless of their assigned group to assess outcomes (baseline, mid-intervention and post-intervention). These data will be collected using VA Redcap and the data will be entered behind the VA firewall. Upon completion of the intervention, semi-structured

interviews will elicit stakeholder and participant perceptions of health coaches, use of action plans and responses to coach recommendations (see Table 2 for key informant interview topics).

Feasibility outcomes, including recruitment and fidelity (defined below), will be assessed. Based on previous protocols used at the VA, the phone calls will be audio recorded and 20% of the sessions will be assessed using a fidelity checklist to ensure that the intervention is being delivered as intended. The fidelity checklists (developed based on the most recent intervention manual) will be submitted along with this IRB. The purpose of the fidelity checklists is to verify that the objectives and core concepts for each session are being delivered as intended to the subjects.

We will use a telephone audio recorder (LRX 40 USB), see previously email correspondence with ISO and PO for IRB 16-024 , Aim 1) to record these sessions. Approval from IT to use LRX 40 USB was obtained already for Aim 1 and Aim 2- we will use the same recording device.

[figure not shown]

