Timing of assessments/ data collection: The research staff will screen, identify eligible Veterans for the study, obtain consent (either in person or verbally (over the phone) initially followed by mailed written consent), and complete further screening for eligibility. If the subject is eligible for this study, the research staff will arrange a separate phone call for a baseline assessment via telephone. The baseline interview must be completed within 2 weeks for the participants to proceed to the intervention. This time frame may be extended at the discretion of the study team. Once the baseline visit is complete then the patient will be informed if randomization allocation.

As seen in the Figure below, the health coaches will conduct the once a week session (or every two weeks depending on the session content) sessions (11 in total), delivered via telephone. A research team member, not the individual conducting the intervention sessions, will complete all assessments via telephone using a structured data collections tool at baseline, 5 weeks (mid-point assessment), at 10 weeks (post intervention

session), 6 months and 12 months post-intervention. Those in the Annie texting-pilot will participate for the duration that the MOTIVATE sessions are typically provide to the waitlist control group (8 sessions over 12-20 weeks). The study team will also conduct interviews as outlined above at 6 months and 12 months to obtain feedback regarding implementation and sustainability of the behaviors learned. The data from these assessments will be entered into a VA Redcap database <https://vhacdwweb05.vha.med.va.gov/> that is housed behind the VA firewall on secure research folder on VA servers:

<\\v17.med.va.gov\\v17NTX\\Services\\Research\\[name]-Research>. All data entered into Redcap is de-identified. Following the physical activity session, the health coach or research staff will obtain daily versus weekly step counts that the subject will read out over the phone. Total steps taken will be documented within 1 week, and then at during subsequent health coaching sessions as well as the 10 week assessment by research staff.

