Proposed Analyses: Exact binomial method will be used to estimate rates of recruitment, intervention adherence, retention, and drop-out along with the corresponding 95% confidence intervals. Multiple levels of treatment retention will be defined, including partial intervention completion (% who do not complete all sessions), intervention dropout (% who dropout of intervention but continue to do assessments), research dropouts (% who remain in intervention, but do not complete assessments), and intervention + research dropouts (% who do not complete intervention or assessments). We will further break down the enrollment and retention calculations by examining enrollment/retention differences by treatment group, health coach, gender, age, race/ethnicity, and initial cLBP and depression severity using cross-classification tables.

As exploratory analyses, pre-post improvement in disability (RMDQ) and depression (PHQ-9) scores, as well as secondary and intermediate outcomes, from baseline to 3 months will be compared based on a two-sample t-test or Wilcoxon rank-sum tests between the two groups. The difference in improvement will be estimated and the 95% confidence interval will be reported. We will estimate the preliminary effect size and variance of effect for the above outcomes. Linear mixed models will be used to assess whether there is a difference in the above outcomes over time within and between the two groups. We will include distance (in miles) from a VA facility as a covariate in the exploratory outcome analyses, as suggested by reviewer.

We will describe, for the subset of subjects receiving the intervention, whether physical activity (proximal outcome) and clinical outcomes (disability and depression scores) change over time based on the 1) proportion of the total sessions completed, and 2) the proportion of individual sessions completed. This will help us estimate optimal dose of the intervention (for example, whether completion of 4 vs. 7 vs. 8 of 10 sessions produces similar outcomes) and may inform which specific sessions are absolutely critical. SAS (version 9.3, Cary, NC) statistical software will be used.

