The **third** recruitment strategy involves referral directly from a provider. [name] will provide a flyer to be posted in PRIME, ambulatory care, Rheumatology or PM&R clinics (see attached to this IRB protocol submission) outlining the eligibility criteria and brief synopsis of the study. If the Veteran is interested in learning more and participating in this study, he or she may call [name] or the study team at the number provider on the flyer, or, with the HIPAA waiver, the provider may notify [name] to call the Veteran (as additional cosigner on the clinic note). When/if [name] or her research team speaks with the Veteran (preferably in person but may be over the telephone if more convenient for the Veteran), we will describe the study, risks and potential benefits and obtain consent, also for audio-recording. The eligibility criteria will be assessed and confirmed over the phone or in person (whichever more convenient for Veteran) via self-report and review of CPRS data.

Following verbal consent and further screening for eligibility, if patient is eligible and interested, we will mail a consent form, HIPPA Authorization form, and VA Form 10-3203, Consent for Use of Picture and/or Voice to patients. These forms will include pre-paid postage for participants to sign and mail back to the VA (research office). The research team will then sign the consent form and enter a research consent and enrollment note into CPRS. This CPRS note will serve as the notification to the PCP that the patient is enrolled in this study. At this time, a binder with the intervention manual material will be sent to the subject's home. This manual is intended for the patient to follow along with the health coach during phone calls. It will also contain the activity trackers that he/she will use in between session to track activity, step counts, and impact on pain and depression. We will mail out appointment letters before each intervention visit. The patients will also be called prior to the scheduled phone calls as a reminder. During Aim 2, we learned that some patients are forgetful about the timing of the phone calls which causes delays- these phone call reminders were helpful.

Prior to audio recording sessions and conducting the telephone based behavioral intervention, study staff will obtain consent and HIPPA authorization from all subjects. All data will only be accessible to authorized study personnel and will be stored on password protected and secure networks.

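### Control-arm exposure is left open in two places: the Section 17 binder mailing has no arm condition, and the exploratory mixed model names no last visit although controls are offered the programme

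*Combined protocol and SAP*

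**What the plan says.** **Binder.** In Section 17, the mailed-consent text after the third recruitment method has staff sign the consent form and enter a note in the record that "the patient is enrolled in this study. At this time, a binder with the intervention manual material will be sent to the" subject's home. No arm is named and randomisation is not mentioned. The same paragraph continues: "We will mail out appointment letters before each intervention visit. The patients will also be called prior to the scheduled phone calls". Section 12 (Randomization) has a nearly identical binder sentence, but places it after the baseline assessment and random assignment and restricts it to the subject's "home if randomized to the intervention arm. This manual is intended for the patient to follow along" with the coach. Section 12 also says of controls that "they will continue receiving usual care for both cLBP and depression, but not the active intervention".

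**Mixed model.** Section 13 (Proposed Analyses) first gives an exploratory comparison of improvement "from baseline to 3 months will be compared based on a two-sample t-test or Wilcoxon rank-sum tests between the two groups". The sentence on modelling reads "Linear mixed models will be used to assess whether there is a difference in the above outcomes over time within and between" the two groups; it lists no visits. Section 12 schedules assessments at baseline, 5 weeks, 10 weeks, and 6 and 12 months post-intervention, and Section 11 repeats the two late ones. Section 5 offers controls the programme once the active group has finished its sessions and assessments, without saying which assessments. Section 12 (Annie phase II) describes controls who have completed the end assessment and been offered the sessions.

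**The concern.** Both gaps bear on whether the control arm is still a control when it is compared with the intervention arm.

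The binder holds the manual and activity trackers, and physical activity is a measured proximal outcome. Staff who follow Section 17 literally would send it to controls as well. That could blur every post-baseline comparison, including the baseline-to-3-month one that the plan most naturally uses for its preliminary effect size.

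The mixed model raises a later problem. If it takes in visits after controls have been offered the programme, a between-group difference at those visits no longer estimates intervention versus waitlist. It estimates an immediate versus a delayed offer and would tend to understate an effective intervention. The pilot is meant to inform a later effectiveness trial, so a diluted late estimate could be carried forward under the wrong name.

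**Working it through.** The plan gives no power calculation, effect size, waitlist uptake or binder effect, so it has no figure to reproduce and neither bias can be computed. What can be checked is the text and the timing.

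**Step 1. The binder passages side by side**

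| | Section 17 | Section 12, Randomization |
|---|---|---|
| Trigger | Consent signed, enrolment note entered | Baseline done, subject randomised |
| Recipient | The subject, no arm condition | Intervention arm only |

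The two differ on both rows, and Section 17 also conflicts with the Section 12 description of the control condition. Section 18 refers the reader to both sections for recruitment and consent, so neither can be set aside as background.

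Whether Section 17 puts the binder ahead of baseline is an inference. Section 12 (Timing) has staff obtain consent, finish screening and then "arrange a separate phone call for a baseline assessment via telephone. The baseline interview must be completed within 2 weeks", which suggests that consent comes first. It does not say that the signed form must be back, or the enrolment note entered, before that call.

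**Step 2. When would controls be treated?**

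Inputs:
- E, week of the end assessment: nominally 10 (Section 12). Section 11 lets delivery run 10-20 weeks, so E = 10 to 20 is assumed.
- L, length of the course as given to waitlist subjects: 12-20 weeks (Section 12, Timing).
- Late visits: 6 and 12 months post-intervention, taken as E + 26 and E + 52 weeks.
- Assumption: the offer opens at the end assessment and the control starts at once.

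| | E = 10 | E = 20 |
|---|---|---|
| Course ends, E + L | 10+12 = 22 to 10+20 = 30 | 20+12 = 32 to 20+20 = 40 |
| 6-month visit, E + 26 | 36 | 46 |
| 12-month visit, E + 52 | 62 | 72 |

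Overall, the course ends at about week 22-40 and the 6-month visit falls at about week 36-46. Where a control's visit is counted from the same E, it falls 26 − 20 = 6 to 26 − 12 = 14 weeks after the course ends. If the control's visit keeps to the week-10 calendar (week 36) but the offer opens only at week 20, a 12-week course ended 36 − 32 = 4 weeks earlier and a 20-week course has 40 − 36 = 4 weeks left. Controls who take up the offer would be largely or fully treated by then.

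Under this timing, 2 of the 4 post-baseline assessments (6 and 12 months) fall after the offer. It is 1 of 3 if the 12-month contact is only the interview of selected subjects described in Section 19. If the offer waits until after the 12-month assessment, none do.

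**Step 3. Which visit is 3 months?**

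Three months is about 52/4 = 13 weeks. The assessment schedule has no such visit; the nearest is week 10, 3 weeks earlier. If week 10 is meant, and it precedes the offer, crossover does not touch the two-sample comparison.

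**The case against.** **On the binder.** The Section 17 wording looks carried over. Section 6 still ends with Aim 2 instructions ("please focus only on Aim 2. Aim 1 has already been IRB approved (#16-024). A separate IRB submission will address Aim 3"), and Section 17 points back to Section 12 for recruitment. The manual is for following along with a coach, whom controls do not have during the control period, and letters before intervention visits have no application to someone with no such visits. This stands as an explanation: intervention subjects were probably meant. It does not remove the conflict, because the text does not say so.

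A reader might infer that Section 17 sends the binder to every subject before baseline. The documents do not support that. The sentence appears only after the third recruitment method; the parallel text for the first method and the in-person route have no binder sentence. The order relative to baseline is, as shown above, not stated.

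**On the model.** The narrower reading has real support. The outcomes it refers back to were introduced with the 3-month range. Section 12 assigns the extended data to differential attrition and formative evaluation and elsewhere lists outcome calls only up to post-intervention. Section 13 heads its variable list with pre-screen, baseline, mid and end assessments. But Section 12 also says the long follow-up is there to learn how behaviours are sustained, a 6-month assessment is scheduled, and nothing excludes it from the model.

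**On timing.** The trigger in Section 5 is worded for the active group as a whole. If it is applied that way, overlap depends on each control's enrolment date and cannot be computed. Figure 3, not available in the text reviewed, may fix the crossover time; it is less likely to say which visits the model uses.

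**On the contrast.** Immediate versus delayed offer is a valid randomised comparison. That is right; the objection is only to reporting it as intervention versus waitlist.

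**Conclusion.** Both gaps are real and minor. The two binder passages contradict each other on timing and arm, and following Section 17 as written would give controls intervention material, possibly before baseline. The mixed model has no stated last visit, and on the most natural reading of the waitlist offer the late visits come after controls can be treated.

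It would go too far to say that the plan does analyse post-crossover data as a controlled comparison, or that the 3-month result is compromised by crossover. The first is left open, and the second does not follow if 3 months means the end assessment before the offer.

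The week ranges are illustrative and rest on an offer made at the end assessment and taken up at once. The direction of the late bias assumes an effective intervention and some uptake by controls; its size, like that of any binder effect, cannot be computed. Severity is limited because the affected analyses are exploratory and the primary outcomes are feasibility measures.

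**What to change.** 1. Reconcile the Section 17 binder text with the two Section 12 passages, so that one statement says when the binder is sent and to which arm.
2. State when the waitlist offer opens relative to each scheduled assessment.
3. List the visits in the mixed model. Limit the intervention-versus-waitlist contrast to scheduled visits up to the end assessment that precedes the offer. Make the cut by scheduled visit, not by each control's own crossover date, which would select data on a post-randomisation event.
4. Say which scheduled visit 3 months means.
5. Report 6- and 12-month outcomes within arm, or labelled as immediate versus delayed offer.

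The cost is protocol and analysis wording. The downside is that no randomised intervention-versus-waitlist outcome contrast is claimed at 6 or 12 months.
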